Overview of the Approach: A total of 90 subjects (70 subjects with chronic HIV-1 infection and 20 HIVnegative control subjects) will be recruited (See Figure 2). For the neurological substudy, an additional 15 HIV-negative control subjects will be recruited and complete Visit A and Visit B (see Figure 1b, not shown in Figure 2 flowchart). Ninety subjects will complete **Baseline Study Part 1** of the cross-sectional study. **Baseline Study Part 2** will be performed in a subset of 60 HIV-infected patients and 10 HIVnegative controls. The 60 HIV-positive patients who complete Baseline Studies Part 1 and Part 2 will enter the **Randomized Study of Teduglutide vs. Placebo**. The tests and procedures obtained during the Baseline Studies Part 1 and Part 2 for these 60 HIV-positive participants will serve as the baseline measurements for the randomized study (they are not repeated) in order to minimize risk from exposure to study procedures for the participants and to maximally utilize the study data.

Having the control group will help us establish whether assessed relationships between GI epithelial integrity, microbial translocation, immune activation, and cardiovascular imaging markers are HIV-specific. Adding the neurological substudy control group (n=15) will help us potentially identify a HIV-

specific, cardiovascular and inflammatory link to cognitive impairment and depression. The control group can also serve as a comparison group with which to compare the HIV patients.

Figure 2

After all subjects have completed the study, transcriptomic profiling by RNA-Seq will be performed in 7 HIV+ participants with greatest degree of coronary disease seen on CTA vs. 7 HIV+ participants without and 7 HIV+ participants with the greatest degree of bacterial translocation vs. 7 HIV+ participants with the least amount of microbial translocation.

Participants will be recruited from the Boston area from infectious disease clinics, HIV community centers and also via IRB-approved advertisements. Patients will also be recruited via referral by primary care providers, infectious disease providers, newspaper advertisement, posted flyers, and Partners subject recruitment broadcast. After obtaining informed consent, baseline measurements and studies will be performed.

Inclusion criteria for HIV-infected participants:

- 1. Men and women age 21-65 with previously diagnosed HIV disease

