The Baseline Study Part 1 includes 10 patients with HIV and 10 patients without HIV and does not involve a colonoscopy, CT scan, or PET scan. Some of the exclusion criteria listed above are only relevant for participants undergoing a colonoscopy, CT scan, or PET scan. Patients participating only in the Baseline Study Part 1 will be excluded based on the following criteria only:

- 1. History of clinically significant gastrointestinal disease including but not limited to: colon cancer, intestinal obstruction, ulcerative colitis, Crohn's disease, or history of C. difficile within the past 3 months
- 2. First-degree relative with history of colon cancer
- 3. Active gall bladder, biliary or pancreatic disease
- 4. Female subject who is pregnant, nursing or less than 8 weeks post partum.
- 5. Use of any immunomodulatory agents within 30 days prior to study enrollment
- 6. Renal disease or creatinine >1.5 mg/dL (contrast will be administered during CT angiography of the heart)
- 7. History of myocardial infarction, decompensated cirrhosis, or any other condition that in the opinion of the investigator will compromise ability to participate in the study
- 8. Currently taking anticoagulants including but not limited to: heparin (Hep-Lock, Hep-Pak), Hep-Pak CVC, Heparin Lock Flush), warfarin (Coumadin), tinzaparin (Innohep), enoxaparin (Lovenox), danaparoid (Orgaran), dalteparin (Fragmin), clopidogrel (Plavix)
- 9. Subject taking any of the following medications: systemic steroids (inhaled or nasal steroid therapy is permitted), interleukins, systemic interferons (e.g. local injection of interferon alpha for treatment of HPV is permitted), systemic chemotherapy including oral chemotherapeutic agents, methotrexate, octreotide, growth hormone, antiarrhythmics including digoxin, antiepileptics, immunosuppressants, vancomycin, rifampin, aminoglycosides, clonidine, prazosin, lithium and ritonavir-boosted lopinavir (Kaletra).
- 10. Subjects receiving high dose statin therapy (a stable low or moderate dose of statin is permitted)
- 11. Initiation of statin therapy or change in statin dose <90 days prior to entry
- 12. Body weight greater than 350 lbs
- 13. Active illicit drug use
- 14. History of malignancy in the last 5 years, with the exception of surgically cured non-metastatic non-melanoma skin cancers

- 15. Prior recipient of a HIV vaccine
- 16. Currently receiving pre-exposure prophylaxis (PrEP)

IV. Subject Enrollment

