[name] of the MGH Biostatistics Center has provided biostatistical consultation regarding power calculations and design for the proposed studies. [name] biostatistical support will continue to be readily available for randomization, data analysis, and manuscript preparation.

Statistical Analysis Plan:

Baseline Study Part 1: Biomarkers, Immunology and Intestinal Permeability Studies and **Baseline Study Part 2: Colonoscopy, Cardiac CTA and FDG-PET/CT Studies (Aim 1A):** The statistical approach to assess correlations between intestinal permeability and microbial translocation with innate immune activation and cardiovascular disease. For mechanistic modeling, we will perform bivariate exploratory analysis followed by multivariate linear regression models to explain the impact of microbial translocation on cardiovascular inflammation.

Univariate analysis: To identify relationships between GI epithelial integrity, markers of innate immune activation and markers of microbial translocation with cardiovascular markers of vascular inflammation (TBR measured by FDG-PET) and atherosclerosis (segments with plaque) in HIV-infected patients, we plan to use linear correlation coefficients for continuous predictor variables (Pearson correlation coefficients if variables are normally distributed or Spearman correlation coefficients if their distributions are non-normal) to assess bivariate relationships between cardiovascular imaging measurements and measured covariates hypothesized to be associated with atherosclerosis development and vascular inflammation.

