*Multivariate modeling:* For outcomes TBR and plaque, to control for potential confounders, multivariate linear regression modeling will be used to identify factors independently associated with increasing TBR and increasing number of atherosclerotic plaque lesions. Similar methods will be applied for neurocognitive score and mood assessment to cerebral FDG-PET/CT. Model variable selection will be based on "change-in-estimate" method⁵⁸. Candidate covariates to be chosen for entry into our model include all covariates significant on individual univariate models (p<0.05), potential confounders, and biologically plausible covariates with established relationships to atherosclerosis. Colinearity among covariates will be identified and redundant covariates will be excluded from the model. Confounders will be identified by observing changes in effect estimate β ; colinearity will be identified by observing changes in effect estimate β ; as well as by using Variance Inflation Factor criterion. Regression diagnostics will be used to check if model assumptions are met⁵⁸. We will control for age, gender, race, smoking, lipids, diabetes mellitus, WRAT 4 reading versus educational years, and hypertension in addition to other potential confounders identified by methods above.

Between group comparisons: We will also assess differences in microbial translocation, mucosal immunity and GI permeability markers among those with coronary atherosclerosis vs. those without atherosclerosis and in those with elevated TBR (>1.8) vs. those without elevated TBR. 2 group comparisons will be performed using Student's T-test if the outcome variable is normally distributed. Distributions will be tested for normality using the Wilk-Shapiro test and examination of the histogram distributions. If the outcome variable is not normally distributed, we will consider appropriate transformation to approximate a normal distribution. Alternatively, if distributions are non-normal despite the applied transformation, we will use nonparametric Wilcoxon rank sum test to compare the 2 groups. All tests will be 2-sided, and a p < 0.05 will be considered statistically significant.

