Sample Size Determination: With 70 HIV-infected patients and 20 uninfected controls, we can detect a bivariate correlation Pearson's coefficients of at least 0.58, 0.33, and 0.29 can be detected at a 5% significance level with 80% power within uninfected, infected, and both the uninfected and infected subjects respectively. The detectable effect sizes of markers between elevated - and without elevated TBR groups will depend on the distribution of the observed TBR and the markers' distributions. If the rate of elevated TBR is 50% among the whole cohort of 70 patients, then an effect size with Cohen's effect size d>0.68 can be detected by a two-sided independent samples t-test at a 5% significance level with 80% power.

RNA Sequencing Subset (Aim 1B):

Statistical Analysis Plan: The BioConductor package LIMMA will be used to identify genes which are differentially expressed between the two compartments. Holm's and Benjamin-Hochberg methods will be applied for correcting multiple testing. *Sample Size Determination*: For *RNA-Seq* analysis using 7 patients with CVD and 7 without, there will be 27,000 genes to be included in the initial testing of which about 140 genes are expected to be differentially expressed significantly with a two to three times of the standard deviation of the fold difference in the expression levels. With a targeted false discovery rate (FDR) of 20% or less, the power to detect at least 112 differentially expressed genes significantly with an effect size of 2.7×SD with p<0.0011 (i.e., multiple testing adjusted alpha=0.0011) will be at least 80%.

Randomized Study of Teduglutide vs. Placebo (Aim 2):

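### The detectable correlation of 0.33 in HIV-infected patients uses n=70, but correlations with TBR, plaque or biopsy have at most 60: power at 0.33 is about 74% and detectable r about 0.35

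*Combined protocol and SAP*

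**What the plan says.** The Sample Size Determination for Aim 1A starts from 70 HIV-infected patients and 20 uninfected controls. It states that "coefficients of at least 0.58, 0.33, and 0.29 can be detected at a 5% significance level with 80% power"; the three values are for the controls, the HIV-infected patients and the two groups pooled, in that order. No separate figure is given for participants who have imaging.

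The Univariate analysis paragraph of the Aim 1A Statistical Analysis Plan names the outcomes to be correlated with the gut, immune and translocation markers: "cardiovascular markers of vascular inflammation (TBR measured by FDG-PET) and atherosclerosis (segments with plaque) in HIV-infected patients". It uses Pearson coefficients, or "Spearman correlation coefficients if their distributions are non-normal".

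The Research Design text places colonoscopy, cardiac CTA and FDG-PET/CT in Baseline Study Part 2. Section III (Subject Selection, Overview of the Approach) says that Part 2 "will be performed in a subset of 60 HIV-infected patients and 10 HIVnegative controls". The criteria for Part 1-only participants in the same section confirm the remainder: that group "includes 10 patients with HIV and 10 patients without HIV and does not involve a colonoscopy, CT scan, or PET scan".

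The sample size paragraph then gives a detectable Cohen's d of 0.68 for elevated against non-elevated TBR, based on a cohort of 70.

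**The concern.** The correlations that the analysis plan names for HIV-infected patients all have an imaging outcome on one side. TBR and plaque exist only for Part 2 participants, as do biopsy measures. The only published sensitivity figure for HIV-infected patients uses 70, a count that includes 10 people with no scan and no colonoscopy.

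A reader would naturally take 80% power at r=0.33 to apply to TBR and plaque, and could read too much into a null result. TBR and plaque are also the outcomes of the multivariate models, where a univariate p below 0.05 is one of three routes by which a covariate becomes a candidate. Lower univariate power therefore makes that route slightly less reliable.

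The same question arises for the control group, because Section III wants controls to help show whether relationships among GI integrity, translocation, "immune activation, and cardiovascular imaging markers are HIV-specific".

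**Working it through.** **Inputs.** Two-sided 5% level (Between group comparisons paragraph: all tests 2-sided). Target power 80% and r = 0.58, 0.33, 0.29 (Sample Size Determination). Part 1 counts: 20 uninfected, 70 infected, 90 combined. Part 2 counts: 60 infected, 10 parent-study controls (Section III).

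**Formulas.** Fisher z approximation:
- power = Φ(atanh(r)·√(n−3) − 1.960)
- detectable r = tanh((1.960 + 0.842)/√(n−3))

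Exact check: power of the t-test for Pearson r under bivariate normality (noncentral t averaged over a chi-square with n−1 df).

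**Step 1: reproduce the stated figures.**

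| r | n | Fisher z power | Exact power |
|---|---|---|---|
| 0.58 | 20 | 78.0% | 80.1% |
| 0.33 | 70 | 80.1% | 80.7% |
| 0.29 | 90 | 79.5% | 80.0% |

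For r=0.33, n=70: atanh(0.33) = 0.3428; 0.3428 × √67 = 2.806; Φ(2.806 − 1.960) = 80.1%. The three values rest on the full Part 1 counts. A one-sided test would give 0.295 at n=70, so 0.33 is two-sided.

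**Step 2: HIV-infected patients with imaging, n=60.**
- Fisher z: 0.3428 × √57 = 2.588; Φ(2.588 − 1.960) = 73.5%.
- Exact: 74.2%. Simulation with 200,000 replicates: 74.1%.
- Detectable r: tanh(2.802/√57) = 0.355 by Fisher z; 0.352 exact.
- Smallest n for 80% at r=0.33 (exact): 69 (80.1%); n=68 gives 79.5%.

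**Step 3: chance of missing the univariate p<0.05 route at a true r of 0.33.** 1 − 0.742 = 26% at n=60, against 1 − 0.807 = 19% at n=70.

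**Step 4: control-only and pooled imaging correlations (exact).** The answer depends on which imaged controls count. The 15 HIV-negative neurological-substudy controls also have CTA and FDG-PET (Visits A and B).

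| Imaged controls counted | Controls: n, detectable r | Pooled: n, detectable r |
|---|---|---|
| Parent study only | 10, 0.76 | 60+10 = 70, 0.33 |
| Plus neurological substudy | 25, 0.53 | 60+25 = 85, 0.30 |
| Stated in the plan | 20, 0.58 | 90, 0.29 |

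**Step 5: the d figure.** Two-sample t-test, 80% power, half the cohort with elevated TBR: 35 against 35 gives d = 0.679, which matches 0.68; 30 against 30 gives d = 0.736.

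**The case against.** The strongest defence is that nothing has been miscalculated. The sample size paragraph states its denominators, speaks of a bivariate correlation in general, and does not name TBR or plaque. Aim 1A also covers permeability and translocation against innate immune activation, and the procedures section plans I-FABP, LPS and sCD14 in 70 plus 20 participants. That stands: 0.33 is correct for Part 1 pairs. What remains is that no correlation figure is given for the imaging outcomes that the univariate analysis names.

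It is also fair to say that the consequence is small. The plan calls the bivariate work exploratory, attaches no threshold to 0.33, and lets confounders and biologically plausible covariates enter the models without univariate significance.

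A reader might infer that control-only imaging correlations are certain to be far weaker than stated, at 0.76 rather than 0.58. The documents do not support that as a flat statement. If the 15 neurological-substudy controls also have the marker concerned, the value is about 0.53, slightly better than stated. Their visits list no permeability study or colonoscopy, and I-FABP and LPS are planned in 20 controls. Yet MCP-1, sCD163 and sCD14 are to be measured in all, so the position differs by marker and is not settled.

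A reader might likewise conclude that d of 0.68 is wrong, or that it is safe. Neither follows. The 70 equals 60 plus 10 imaged participants, but it could also mean the 70 HIV-infected patients named earlier in the paragraph.

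Unevaluable scans or Spearman coefficients would lower power further. Those losses depend on assumptions and are not part of a denominator error in a statement about Pearson correlation.

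**Conclusion.** The point holds for HIV-infected correlations with TBR, plaque or biopsy. The stated 80% power at r=0.33 is about 74% at n=60, roughly six points short, and the detectable r is about 0.35 rather than 0.33. This assumes Pearson correlation, bivariate normality, full recruitment and every scan evaluable, so 74% is an upper limit under that model.

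The shortfall is modest. It does not make the Part 1 figures wrong, and it does not bear on Aim 2, which has its own sample size calculation. The control and pooled imaging figures, and the cohort behind d of 0.68, are unclear rather than shown to be wrong. They need a statement of who is counted.

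**What to change.** In the Aim 1A Sample Size Determination:

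1. Limit 0.58/0.33/0.29 to pairs of variables both measured in Part 1 (n=20/70/90).
2. For HIV-infected correlations with TBR, plaque or biopsy, state a detectable r of about 0.35 (Pearson, n=60, all scans evaluable).
3. If control-only or pooled imaging correlations will be reported, say which imaged controls count. With the 10 parent-study controls the values are about 0.76 (controls) and 0.33 (pooled n=70). With the 15 substudy controls added, for markers they have, they are about 0.53 (n=25) and 0.30 (pooled n=85).
4. Say which 70 participants the d of 0.68 refers to. Keep it if they are the 60 HIV-infected plus 10 controls with imaging; replace it with about 0.74 if only the 60 imaged HIV-infected patients are compared.

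The cost is rewording a few sentences and accepting a slightly less favourable sensitivity for imaging correlations. No patients or procedures are added.

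### The plan wants to know whether marker relationships are HIV-specific, but names no test of a difference between HIV groups and no HIV term

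*Combined protocol and SAP*

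**What the plan says.** Section III, Overview of the Approach, says the controls are there to help establish "whether assessed relationships between GI epithelial integrity, microbial translocation, immune activation, and cardiovascular imaging markers are HIV-specific". The same paragraphs put everyone through Baseline Study Part 1 (70 HIV-infected, 20 controls). Part 2, which supplies colonoscopy, CTA and FDG-PET, is "performed in a subset of 60 HIV-infected patients and 10" controls. A further 15 HIV-negative subjects in the neurological substudy also have CTA and FDG-PET.

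The Statistical Analysis Plan for Aim 1A then provides:

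- **Univariate analysis:** correlations of imaging measures with markers, in the HIV-infected patients.
- **Multivariate modeling:** linear regression for TBR and plaque. The named covariates begin "We will control for age, gender, race, smoking, lipids, diabetes mellitus" and go on to the WRAT 4 reading or education variable and hypertension, plus other confounders found by the selection procedure. HIV status and an interaction with it are not named.
- **Between group comparisons:** by presence of atherosclerosis and by TBR above 1.8, not by HIV status. "All tests will be 2-sided, and a p < 0.05 will be considered statistically significant".
- **Sample Size Determination:** the paragraph opens "With 70 HIV-infected patients and 20 uninfected controls". It states that "Pearson's coefficients of at least 0.58, 0.33, and 0.29 can be detected", taking 5% significance and 80% power. The three values apply, in that order, "within uninfected, infected, and both the uninfected and infected subjects respectively".

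The plan states no rule for calling a relationship HIV-specific.

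**The concern.** Whether a relationship is specific to HIV is a question about a difference between two groups. The plan gives one correlation per group and one for the groups combined, and none of these measures that difference.

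Two errors become possible. First, a relationship that is significant in 70 patients and not significant in 20 controls invites the reading that it belongs to HIV, although the control group is simply too small to show it. Second, if the groups are pooled without HIV status in the model, a marker and an outcome that both differ by HIV status will correlate even when they are unrelated within each group. The background and aims expect translocation and immune activation to be raised in HIV, so such shifts are plausible.

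The authors already use the needed device elsewhere: the Aim 2 analysis plan has a time-by-group interaction. Aim 1A has no counterpart.

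**Working it through.** **Inputs from the documents.** Two-sided 5% tests; 70 and 20 subjects for Part 1 markers; 60 and 10 for Part 2 imaging; 15 further imaged controls whose use in Aim 1A is not stated (60 and 25 if they join); detectable correlations 0.58, 0.33 and 0.29 for n = 20, 70 and 90.

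**Assumptions, not in the documents.** A true correlation ρ that is the same in both groups, anchored at 0.33 and varied; the reading rule of p < 0.05 in HIV and p ≥ 0.05 in controls; for pooling, a shift of d SD by HIV status in both variables and no relationship within groups.

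**Step 1: reproduce the plan's figures.** Let t be the 97.5% t quantile on n − 2 df, r_c = t/√(t² + n − 2), z_c = atanh(r_c) and z_r = atanh(r) + r/(2(n − 1)). Then power = Φ((z_r − z_c)√(n − 3)) + Φ((−z_r − z_c)√(n − 3)).

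- n = 20, r = 0.58: (0.6777 − 0.4769) × 4.123 = 0.828, power 79.6%.
- n = 70, r = 0.33: (0.3452 − 0.2397) × 8.185 = 0.864, power 80.6%.
- n = 90, r = 0.29: (0.3002 − 0.2103) × 9.327 = 0.839, power 79.9%.

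The stated 80% is confirmed in all three cases.

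**Step 2: significant in HIV only, when the true correlations are equal.** The groups are independent, so the rate is power(HIV n) × [1 − power(control n)].

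- ρ = 0.33, 70/20: 0.806 × (1 − 0.303) = 56%.
- ρ = 0.33, 60/10: 0.741 × (1 − 0.157) = 62%.

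The same formula over a range of ρ:

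| ρ in both groups | 70/20 | 60/10 | 60/25 |
|---|---|---|---|
| 0.10 | 12% | 11% | 11% |
| 0.20 | 33% | 31% | 28% |
| 0.30 | 54% | 56% | 45% |
| 0.33 | 56% | 62% | 46% |
| 0.40 | 53% | 70% | 43% |
| 0.50 | 36% | 66% | 25% |

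The rate exceeds 50% only for ρ of about 0.275 to 0.42 at 70/20 (maximum 57%) and about 0.275 to 0.61 at 60/10 (maximum 71%). At 60/25 it never exceeds about 47%. Simulation of the sampling distribution of r (400,000 draws) agrees with the 70/20 and 60/10 columns to within about a percentage point.

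**Step 3: a direct test.** Fisher z difference with SE = √(1/(n₁ − 3) + 1/(n₂ − 3)). At a common ρ of 0.33 it rejects 5.0% of the time in simulation, at both 70/20 and 60/10.

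Power against a control correlation of 0:

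- 70/20: SE = √(1/67 + 1/17) = 0.272. For 0.33, 0.343/0.272 = 1.26, power 24%. For 0.40, 0.424/0.272 = 1.56, power 34%.
- 60/10: SE = √(1/57 + 1/7) = 0.401. For 0.33, 0.343/0.401 = 0.86, power 14%. For 0.40, 0.424/0.401 = 1.06, power 18%.

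**Step 4: pooling without HIV status.** With control fraction p, the induced correlation is p(1 − p)d²/(1 + p(1 − p)d²), put into the Step 1 power formula at the pooled n.

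| Shift d in both variables | 70/20: induced r | 70/20: false positives | 60/10: induced r | 60/10: false positives |
|---|---|---|---|---|
| 0.5 SD | 0.041 | about 7% | 0.030 | about 6% |
| 0.8 SD | 0.100 | about 15% | 0.073 | about 9% |
| 1.0 SD | 0.147 | about 28% | 0.109 | about 15% |

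The nominal rate is 5%.

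**The case against.** The strongest reply is that the plan never says separate p-values will decide specificity. The three correlations stand in a sample-size paragraph, and the overview says only that controls will help. That is correct, so every rate in Step 2 is conditional on a reading rule that the documents leave open. What stands is that they offer no other rule.

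A reader might infer that equal correlations would be called HIV-specific more than half the time. The documents do not support that as a general statement. It needs the unstated rule and a true correlation in a middle band, and it fails throughout if the 15 substudy controls join the imaging analysis. Those 15 could enter only relationships between blood markers and imaging, since their two visits include no permeability study or colonoscopy.

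A reader might also infer that the regressions are confounded by HIV status. That too goes beyond the text. The univariate imaging analysis is confined to HIV-infected patients, and the regression section does not say that controls enter. In an HIV-only model the term is rightly absent. In a pooled model, the open clause on other confounders could admit HIV status. A main effect would remove the confounding but would still not test specificity. TBR and plaque also have 60 and 10 subjects from Part 2, so the smaller Step 4 rates apply to them.

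Finally, the bivariate work is described as exploratory, and controls play no part in the randomized comparison. That lowers the priority but leaves the gap.

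**Conclusion.** The point holds as an objective without a matching analysis: the controls are meant to show whether relationships are HIV-specific, and no test of difference, HIV term or HIV-by-marker interaction is named.

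If the gap were filled by comparing separate p-values, a shared correlation at the plan's own 0.33 would be mislabelled about 56% of the time at 70/20 and 62% at 60/10, against 5% for a direct test. Even at 0.20 the 70/20 rate is 33%. The pooled problem arises only if groups are combined without HIV status, and its size rests on assumed shifts.

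The Aim 2 primary comparison of TBR change is untouched. This should be fixed before the Aim 1A data are analysed.

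**What to change.** In the Aim 1A Statistical Analysis Plan:

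1. State that HIV-specificity is judged only by the HIV-by-marker interaction, or by a Fisher z difference of correlations, reported with its confidence interval. Choose one in advance: the first compares slopes and the second correlations, and they can disagree when the spread differs between groups.
2. State which analyses pool the groups, and include HIV status in each of them.
3. State which controls enter each relationship, including whether the 15 substudy controls join those between blood markers and imaging.
4. Make no claim of HIV-specificity from separate p-values.
5. Label the question exploratory.

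The cost is a few sentences and one or two model terms. The drawback is low power. For 80% power the test needs a Fisher z difference of 0.76 at 70/20 (for example 0.64 against 0) and 1.12 at 60/10 (for example 0.81 against 0). With 10 controls, a covariate-adjusted interaction will be imprecise. The confidence interval will show this, whereas a non-significant control correlation would conceal it.

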Loss of GI mucosal epithelial integrity and GI tract CD4+ T cells in HIV-infected patients impair the host defense system from intestinal microbes and is proposed to be a cause of immune activation in HIV disease^{32,33}. Structural breakdown of the tight epithelial barrier of the GI tract in HIV and SIV infection leads to translocation of microbes from the GI lumen into the body^{33,34} even among ART-treated HIV patients³². GI tract structural integrity is dependent on the health of the mucosal immune system. One of the hallmarks of HIV infection is a massive depletion of CD4+ T cells in the gut associated lymphoid tissue (GALT). This depletion is accompanied by vigorous mucosal inflammation that impairs gut epithelial barrier function. This loss of epithelial integrity results in the translocation of luminal bacterial products into the systemic circulation which drives systemic immune activation, progressive immune dysfunction, and ultimately disease progression. Thus, HIV immunity within the GALT is central to our understanding of HIV pathogenesis and critical to our efforts to better manage the consequences of chronic infection. In HIV and SIV infection, depletion of Th17 cells, which normally respond to bacterial products, is associated with microbial translocation^{35,36}. HIV viral infection itself may cause epithelial damage due to production of proinflammatory cytokines that can directly induce apoptosis of epithelial cells³⁴. Markers of bacterial translocation into the circulation, plasma lipopolysaccharide (LPS), a bacterial cell wall component, and soluble CD14 (sCD14) are both significantly elevated in chronic HIV infection and plasma LPS levels are found to be related to T cell activation³². Bacterial LPS binds through the CD14 receptor on monocytes and macrophages³⁷ and stimulates activation of the host innate immune system. Furthermore, plasma levels of sCD14 have been demonstrated to independently predict mortality in HIV-infected patients in the SMART trial³⁸ and sCD14 correlated with increases in carotid intimal media thickness¹⁷.

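### Any Aim 1A correlation or model run on HIV-infected and uninfected participants together should condition on HIV status; the plan powers a pooled correlation without doing so

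*Combined protocol and SAP*

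**What the plan says.** **Power.** The Sample Size Determination paragraph for Aim 1A is based on 90 participants: "With 70 HIV-infected patients and 20 uninfected controls". It states that "Pearson's coefficients of at least 0.58, 0.33, and 0.29 can be detected" "at a 5% significance level with 80% power", and assigns the three values as "within uninfected, infected, and both the uninfected and infected subjects respectively". The third value is therefore a plain correlation in the combined sample.

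**Univariate analysis.** Correlation coefficients will be used to "assess bivariate relationships between cardiovascular imaging measurements and measured covariates hypothesized to be associated with atherosclerosis development and vascular inflammation". The same sentence, before those words, limits the analysis of TBR and plaque to HIV-infected patients. The introduction to the Aim 1A plan also promises correlations of permeability and translocation with innate immune activation, and sets no such limit.

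**Multivariate modeling.** The fixed adjustment list reads: "We will control for age, gender, race, smoking, lipids, diabetes mellitus, WRAT 4 reading versus educational years, and hypertension". Other confounders may be added by a change-in-estimate rule. HIV status is not named, and the population for these models is not given.

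**Who is measured.** Section V plans I-FABP, LPS and sCD14 in 70 infected and 20 uninfected participants, and MCP-1, sCD163 and sCD14 in everyone. Section III limits parent-study arterial imaging (Baseline Study Part 2) to 60 infected participants and 10 controls.

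**Expected shift.** Section I says of plasma LPS and sCD14 that they "are both significantly elevated in chronic HIV infection".

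**The concern.** A Pearson test in a mixture of two groups has zero overall correlation as its null. That null is false whenever group membership moves both means in the same direction, even if the two variables are unrelated within each group. Aim 1A asks a different question: whether a person with more translocation has more immune activation than another person of the same HIV status.

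LPS against sCD14 shows the problem most clearly. The protocol treats LPS as a translocation marker, lists sCD14 also as a monocyte/macrophage activation marker, measures both in all 90, and says both are raised in chronic HIV. A raw pooled correlation between them would partly restate the difference between infected participants and controls. Reported as support for the proposed mechanism, it would claim more than the data show. The same applies to a pooled regression that omits HIV status.

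**Working it through.** **Inputs from the plan.** 70 infected, 20 uninfected, 90 combined; alpha 0.05, power 80%; two-sided ("All tests will be 2-sided, and a p < 0.05 will be considered statistically significant"); 60+10 with parent-study imaging. **Assumption.** HIV shifts the two variables by dx and dy within-group SDs. The documents give direction for LPS and sCD14 but no sizes, so a range is used.

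**1. Reproduce the stated figures.** Fisher's z gives r = tanh[(1.960 + 0.842)/√(n − 3)]:
- n=20: tanh(2.802/√17) = 0.591
- n=70: tanh(2.802/√67) = 0.330
- n=90: tanh(2.802/√87) = 0.292

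With a t-based critical value and the usual small bias term, the results are 0.582, 0.328 and 0.290. These match the plan's 0.58, 0.33 and 0.29, so the third figure is an unadjusted correlation at n=90.

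**2. Correlation induced by HIV alone.** Let p be the infected share and q = 1 − p. With zero correlation within each group,

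rho = pq·dx·dy / √[(1 + pq·dx²)(1 + pq·dy²)].

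For 70+20, pq = (70/90)(20/90) = 0.173. With dx = dy = 1, rho = 0.173/1.173 = 0.147. For 60+10, pq = (60/70)(10/70) = 0.122, and rho = 0.122/1.122 = 0.109.

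**3. Rejection rate of the raw pooled test.** Bivariate normal data were simulated with zero within-group correlation and equal shifts in both variables:

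| Shift in both (SD) | rho, 70+20 | Rejects, 70+20 | rho, 60+10 | Rejects, 60+10 |
|---|---|---|---|---|
| 0.5 | 0.041 | 7% | 0.030 | 6% |
| 0.75 | 0.089 | 13% | 0.064 | 9% |
| 1.0 | 0.147 | 28% | 0.109 | 15% |
| 1.5 | 0.280 | 79% | 0.216 | 44% |

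Repeat runs agree to within one percentage point. A hand check at 1 SD for 70+20: atanh(0.147) × √87 = 1.38, and P(Z > 1.96 − 1.38) is about 0.28.

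The 60+10 columns apply only if imaging outcomes were pooled, which the univariate plan does not do.

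**4. Where the inflation disappears.** If HIV shifts one variable by 1 SD and the other not at all, rho = 0 and the pooled test rejects about 5% of the time. Unequal shifts of 0.5 and 1.0 SD give rho = 0.078 and about 12% at 70+20. The test within infected participants alone stays at about 5% throughout.

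**5. After adjustment.** The partial correlation given HIV status rejects about 5% of the time in every scenario. Its detectable value at n=90 is tanh(2.802/√86) = 0.293, against 0.292 unadjusted.

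**The case against.** A reader might infer that the plan would declare a marker related to arterial disease from the pooled test, and that pooled significance would then carry the marker into the multivariable model. The documents do not support either step. The correlations with TBR and plaque are confined to HIV-infected patients, where this artefact cannot arise. The univariate screen that feeds the multivariable model is the one described immediately before it, with that same restriction. The 70+20 rates cannot apply to parent-study imaging outcomes, which exist in only 60+10.

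Further points on the other side are fair:
- The pooled 0.29 appears only as a power figure. No sentence commits to testing a pooled correlation.
- A marginal correlation is a legitimate quantity, only a different one from the within-group association.
- The inflation needs both means to shift, and it is small below about 0.75 SD. Participants are on stable ART with viral load below 200 copies/mL, so the shifts may be modest.
- In an infected-only model HIV status is constant, and leaving it off the list is no defect. In a pooled model, the provision for other confounders could select it.

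All of this limits the point without removing it. The plan powers a pooled correlation, the biomarkers are measured in exactly those 90 people, and the stated wish to correlate translocation with immune activation carries no HIV restriction. Section III also says controls are included to judge whether relationships are HIV-specific, which invites combined analyses. A known design factor sampled 70 to 20 should be prespecified, not left to a data-driven rule.

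**Conclusion.** The point holds for pooled analyses only. A raw correlation in the combined sample, most directly one marker against another, can reject purely because HIV moves both means. A pooled multivariable model without HIV status has the same weakness. At 70+20 the false-positive rate runs from about 7% with shifts of 0.5 SD to about 79% with shifts of 1.5 SD, and exceeds twice the nominal level from roughly 0.75 SD. These rates rest on assumed equal shifts, normal data and no within-group association. The documents supply the direction of shift for LPS and sCD14, but no size.

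The planned TBR and plaque correlations in infected patients are sound in this respect. This is an inexpensive improvement to an exploratory aim, with no bearing on the randomized comparison.

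**What to change.** - State the population for each Aim 1A correlation and for the multivariable models.
- Compute any pooled correlation as a partial correlation given HIV status, using partial Spearman where Spearman would apply.
- Name HIV status as a fixed covariate in any multivariable model fitted to infected and uninfected participants together.
- Restate the third detectable value as a partial correlation (0.293, still 0.29 to two decimals), or delete it if no pooled analysis is intended.
- Keep the separate within-group correlations as they are.

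The cost is a sentence or two and one degree of freedom per pooled analysis. The adjusted estimate no longer counts the between-group part of the association; that part can be reported separately as the difference between infected participants and controls. Adjustment does not by itself show whether a relationship is HIV-specific, which is a separate question about how the association differs by HIV status.
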